ATTACHMENT 2: Multiple Myeloma IMWG Algorithm

PD and Response Algorithm 54767414MMY3008

The issues addressed by the program are:

- 1. Whether or not the disease progressed and date of progression
- 2. The date" of censoring for subjects whose disease never progressed
- 3. Reason(s) for PD
- 4. The date* and category of best and first response
- 5. Duration of response

1. Determination of PD and Relapse from CR

1.1. IMWG Criteria

1.1.1. Progressive Disease

PD is to be used for calculation of time to disease progression and progressionfree survival for all subjects including those experiencing CR.

PD is defined as satisfying any one of the criteria listed below. These are identical to the IMWG criteria as described in the protocol. Further explanations (noted in superscript) pertaining to particular PD criteria are provided in Section 1.2, Clarifications and Modifications.

- Increase ^(1,2,2) of ≥25% in the level of serum M-protein and absolute increase ^(1,2,2) must be ≥0.5 g/dL (5 g/L) ^(1,2,3;1,2,4).
- b. Increase $^{(1.2.2,\ 1.2.18)}$ of \geq 25% in the 24-hour urinary light chain excretion (urine M-protein) and absolute increase $^{(1.2.2)}$ must be \geq 200 mg/24 hours $^{(1.2.3)}$.
- c. Only in subjects without measurable serum and urine M-protein levels: increase $^{(1.2.2)}$ of $\geq 25\%$ in the difference between involved and uninvolved FLC levels $^{(1.2.20)}$ and absolute increase $^{(1.2.2)}$ must be > 10 mg/dL $^{(1.2.3)}$.
- d. Only in subjects without measurable serum and urine M-protein levels and without measurable disease by FLC levels: increase ^(1,2,2) of ≥25% in the level of bone marrow plasma cells percentage and absolute increase ^(1,2,2) must be ≥10% ^(1,2,3).

Day post-randomization for randomized subjects.

- Definite increase (1.2.8) in the size of existing bone lesions (1.2.9) or soft tissue plasmacytomas (1.2.9; 1.2.10).
- f. Definite development of new bone lesions (1.2.11) or soft tissue plasmacytomas (1.2.12, 1.2.13).
- g. Development of hypercalcemia (1.2.14; 1.2.15; 1.2.16) (corrected serum calcium >2.875 mmol/L or >11.5 mg/dL) that can be attributed solely to the PC proliferative disorder.

1.1.2. Relapse from CR

Relapse from CR is to be used for calculation of disease-free survival for subjects experiencing CR.

Relapse from CR is defined as satisfying any one of the criteria listed below (a, b, or c). These are identical to the IMWG criteria as described in the protocols. Further explanations (noted in superscript) pertaining to particular relapse from CR criteria are provided in Section 1.2, Clarifications and Modifications.

- Reappearance of serum or urinary M-protein by immunofixation or electrophoresis (1.2.3; 1.2.7).
- b. Development of $\geq 5\%$ plasma cells in the bone marrow.
- Appearance of any other sign of progression (i.e., new plasmacytomas, lytic bone lesion, or hypercalcemia) (1.2.11; 1.2.12; 1.2.13; 1.2.14; 1.2.15).

1.2. Clarifications and Modifications

In order to allow these rules to be applied consistently and to be programmed, the Sponsor has added certain clarifications and modifications for using the IMWG criteria.

- **1.2.1.** Measurable disease is defined in the protocol by at least one of the following measurement: (1) serum M-protein $\geq 1 g/dL$ ($\geq 10 g/L$) or $\geq 0.5 g/dL$ ($\geq 5 g/L$) for subjects with IgA, IgD, IgE or IgM multiple myeloma; (2) urine M-protein ≥ 200 mg/24h; (3) serum FLC assay: involved FLC level ≥ 10 mg/dL (≥ 100 mg/L) provided serum FLC ratio is abnormal.
- **1.2.2.** The reference point for calculating increase and % of increase for M-protein, FLC and bone marrow plasma cells will be the lowest response value and the "lowest response value" does not need to be a confirmed value.
- **1.2.3.** Requires 2 consecutive (i.e., no intermediate values that do not meet the definition of PD) assessments made at any time before the institution of any new therapy (i.e., subsequent anti-cancer therapy). If a subject has an unconfirmed PD

followed by death due to PD within 30 days of unconfirmed PD, or PD (the same parameter as of initial observed PD) observed within 4 weeks after start of subsequent anti-cancer therapy, the unconfirmed PD will be considered as PD.

- **1.2.4.** If nadir serum M-protein is $\geq 50g/L$ ($\geq 5 \text{ g/dL}$), M-protein increases of $\geq 10g/L$ (1g/dL) is sufficient for progressive disease. It does not require meeting "increase of $\geq 25\%$ in the level of serum M-protein".
- **1.2.5.** Any 2 consecutive increase of serum M-protein \geq 5 g/L (\geq 0.5 g/dL) is consistent with progressive disease, assuming that increase of \geq 25% is met or not applicable, even if the serum M-protein level is below measurable disease threshold.
- **1.2.6.** The baseline value for assessing disease progression is the last pretreatment measurement (it applies to SPEP, UPEP, FLC, plasmacytomas and bone lesions except as noticed in Section 1.2.10). For example, if there is a screening value and a Cycle 1 Day 1 value (prior to start of treatment) for M-protein, the program ignores the screening value and uses Cycle 1 Day 1 as the reference point for assessing PD for the first post-treatment results.
- **1.2.7.** The program disregards serum M-protein and urine paraprotein measurements prior to Day 5 after dosing. These tests are considered too soon after dosing to be regarded as legitimate on-treatment values.
- **1.2.8.** The program computes the date of progression as the earliest date of any of the tests listed in Section 1.1.1 (a, b, e, f or g for subjects with measurable serum or/and urine M-protein; or a, b, c, e, f or g for subjects without measurable serum and urine M-protein) that indicate PD. Similarity, the program computes the date of relapse from CR as the earliest date of any of the tests listed in Section 1.1.2 (a, b, or c) that indicate relapse from CR.
- **1.2.9.** For PD due to bone lesions, the algorithm will rely on information collected on the eCRF regarding skeletal survey (i.e., increase in the size of lytic bone lesions or increase in the total number of lytic bone lesions) and other radiology reports. At any time, study sites may report progressive disease based on an increase in the size or number of lytic bone lesions. The algorithm accepts this determination as definitive.
- **1.2.10.** Plasmacytomas/bone lesions that are first reported during the first week on study are treated as baseline plasmacytomas/bone lesions. The rationale for this rule is that plasmacytomas/bone lesions take time to develop, so anything reported within 1 week of first dose almost certainly existed before the start of study drug.

In the case that no pre-treatment value for plasmacytomas/bone lesion is available, the first post-treatment value is used as baseline.

- **1.2.11.** For plasmacytomas, the Sponsor has defined "definite increase in size" as an increase of over 50% in the sum of the products of the two longest perpendicular diameters when available, using the smallest previous product as the reference point.
- **1.2.12.** New post-baseline bone lesions are evidence of PD. If no baseline bone lesions are available, then any subsequent data that report a bone lesion will be considered as development of new bone lesions.
- **1.2.13.** New post-baseline plasmacytomas are evidence of PD, even if the measurements are not available. If no baseline plasmacytoma data are available, then any subsequent data that report a plasmacytoma will be considered as a "new" plasmacytoma and will be considered as evidence of PD.
- **1.2.14.** Hypercalcemia will be based on corrected calcium values as long as they are available (i.e., corrected calcium values are collected or serum calcium and albumin are collected). If corrected calcium values are not available, free-ionized calcium values will be used if they are available. Hypercalcemia based on free-ionized calcium will be defined as >1.5 mmol/L.
- **1.2.15.** For subjects who have hypercalcemia at baseline, the program will never assess PD due to "development of hypercalcemia". A subject is considered to have hypercalcemia at baseline if he or she meets one of the following criteria:
 - For subjects with corrected calcium values, any corrected calcium value >ULN which occurs on or before Day 4 (relative to first dose).
 - Note: if subject had central and local assessments done on the same day, the central record takes precedence.
 - b. For subjects without corrected calcium values in all visits, but with free-ionized calcium values on or before Day 4, any free-ionized calcium value >ULN which occurs on or before Day 4 (relative to first dose).
- **1.2.16.** For subjects with normal calcium at baseline, if the first PD criteria met is a post-baseline hypercalcemic value, then the following programming algorithm will be applied:
 - a. The program will first search for evidence of progression in other parameters within the following 56 days. If PD is determined in other parameters within the following 56 days, then the subject is assessed as PD. The date of PD is the date of the initial

- hypercalcemic value and hypercalcemia is indicated as the reason or one of the reasons for PD.
- b. If PD is not determined in other parameters within 56 days, the program will search for the next available corrected calcium/free-ionized calcium value. If the second value also meets the criteria for hypercalcemia, the subject is assessed as PD. The date of PD is the date of the initial hypercalcemic value and hypercalcemia is indicated as the reason or one of the reasons for PD.
- If there is no more follow-up calcium value, then the subject is assessed as PD.
- d. Any PD identified through a), b) or c) will be flagged and reviewed by clinical to ensure that hypercalcemia can be attributed solely to the plasma cell proliferative disorder. Hypercalcemia due to other reasons will not be considered as PD in the algorithm.
- **1.2.17.** Descriptive (or non-numeric) results from bone marrow aspirate or bone marrow biopsy will be given a numeric interpretation based on the following conventions:
 - a. Percentage plasma cells reported as a range on the CRF page will be assigned the mean value (i.e., lower range plus upper range divide by 2) that will be analyzed by the programming algorithm (e.g., an amount reported as 10-15% would be interpreted as 12.5%).
 - b. Percent plasma cells reported as <x% will be interpreted as (x-1)% and percent plasma cells reported as >x% will be interpreted as x%.
 - c. Other conventions include:

Reported as: Interpreted as: "Not significantly present" 4% "Sheets of plasma cells not seen" 4%

- **1.2.18.** Imputation of UPEP and SPEP values: If the serum immunofixation result is "Not Detected" and the SPEP value is missing or not done, then SPEP value is treated as 0. If the urine immunofixation is "Not Detected" and the UPEP is missing or not done, then UPEP value is treated as 0.
- 1.2.19. a. Spurious UPEP values are not used in the determination. Determination of a spurious value is as follows: If at least 4 values exist in the neighborhood (+/- 94 days) of the value of interest, the mean and standard deviation of the values is computed (not including the value of interest in the calculation). The value of interest is compared to the mean +/- 3 standard deviations. If the value < mean-3*standard deviation or the value > mean+3*standard deviation then the value is considered spurious. The last two values available for a particular subject

are never considered as spurious. The baseline value for a subject is also never considered as spurious.

- b. If the first PD criteria met is two consecutive UPEP values and subject has started subsequent anticancer therapy, this subject is assessed as PD and date of PD is the date of first UPEP assessment. Otherwise, if the first PD criteria met is two consecutive UPEP values and subject has not started subsequent anticancer therapy, then the following programming algorithm will be applied:
 - The program will first search for evidence of progression in other parameters within the following 94 days. If PD is determined in other parameters within the following 94 days, then the subject is assessed as PD. The date of PD is the date of the initial UPEP value.
 - If PD is not determined in other parameters within 94 days and no more UPEP values are available, then the subject is assessed as PD due to UPEP.
 - 3) Otherwise, the third UPEP value is considered. If the third value meets the criteria for PD, the subject is assessed as PD due to UPEP. If the third value does not meet the criteria for PD, but other parameters indicate PD within the next 94 days, the subject is assessed as PD due to UPEP at the time of the initial UPEP value.
 - 4) Otherwise, the fourth UPEP value is considered. If the fourth value meets the criteria for PD, the subject is assessed as PD due to UPEP. If the fourth value does not meet the criteria for PD, the subject is not assessed as PD due to UPEP. If no fourth UPEP value is available, the subject is not assessed as PD.
- **1.2.20.** Difference between involved and uninvolved FLC level is defined as absolute value of kappa FLC level minus lambda FLC level in the serum.
- **1.2.21.** Development of plasma cell leukemia is considered as disease progression. The date of PD is the date of event onset.

2. Determination of Date of Censoring and Reason for PD

The date of last post-baseline efficacy measure is used as the censoring date for all subjects without progressive disease. Subjects that have no post-baseline efficacy data are censored at the date of randomization for randomized subjects.

The reason(s) for PD is defined as the initial reason(s) that caused the program to indicate PD as well as any other criteria that were met by the time of confirmation of PD. Indicator variables for each reason (SPEP, UPEP, FLC, bone marrow, bone lesion [increase in number, increase in size], extramedullary plasmacytoma [new extramedullary plasmacytoma, increase in size], hypercalcemia and plasma cell leukemia) are created.

3. Determination of Response Category and Duration of Response

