Progressive disease (PD) [†]	 Increase of 25% from lowest response value in any one of the following: Serum M component (absolute increase must be ≥0.5 g/dL), Urine M component (absolute increase must be ≥200 mg/24 hours), Only in subjects without measurable serum and urine M protein levels: the difference between involved and uninvolved FLC levels (absolute increase must be >10 mg/dL) Definite development of new bone lesions or soft tissue plasmacytomas or definite increase in the size of existing bone lesions or soft tissue plasmacytomas Development of hypercalcemia (corrected serum calcium >11.5 mg/dL) that can be attributed solely to the PC proliferative disorder 	

FLC free light chain; PC plasma cell

All response categories (CR, sCR, VGPR, PR, and PD) require 2 consecutive assessments made at any time before the institution of any new therapy; CR, sCR, VGPR, PR, and SD categories also require no known evidence of progressive or new bone lesions if radiographic studies were performed. VGPR and CR categories require serum and urine studies regardless of whether disease at baseline was measurable on serum, urine, both, or neither.

Radiographic studies are not required to satisfy these response requirements. Bone marrow assessments need not be confirmed. For PD, serum M component increases of more than or equal to 1 g/dL are sufficient to define relapse if starting M component is ≥ 5 g/dL.

- * Clarifications to IMWG criteria for coding CR and VGPR in subjects in whom the only measurable disease is by serum FLC levels: CR in such subjects indicates a normal FLC ratio of 0.26 to 1.65 in addition to CR criteria listed above. VGPR in such subjects requires a >90% decrease in the difference between involved and uninvolved FLC levels.
- † Clarifications to IMWG criteria for coding PD: Bone marrow criteria for PD are to be used only in subjects without measurable disease by M protein and by FLC levels; "25% increase" refers to M protein, FLC, and bone marrow results, and does not refer to bone lesions, soft tissue plasmacytomas, or hypercalcemia and the "lowest response value" does not need to be a confirmed value.
- ^a Presence/absence of clonal cells is based upon the kappa/lambda ratio. An abnormal kappa/lambda ratio by immunohistochemistry or immunofluorescence requires a minimum of 100 plasma cells for analysis. An abnormal ratio reflecting presence of an abnormal clone is kappa/lambda of >4:1 or <1:2.

Clinical Relapse

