4.2.1. Definition

PFS is defined as the duration from the date of randomization to either progressive disease, according to the IMWG response criteria, or death, whichever occurs first. Subjects who start subsequent antimyeloma therapies for multiple myeloma without disease progression will be censored at the last disease assessment before the start of subsequent therapies. Subjects who withdrew consent from the study before disease progression will be censored at the last disease assessment before withdrawal of consent to study. Subjects who are lost to follow-up will be censored at the last disease assessment before subjects are lost to follow-up. Subjects who have not progressed and are still alive at the cutoff date for analysis will be censored at the last disease assessment. Subjects without any post-baseline disease assessment will be censored at the randomization.

Determination of dates of PFS event and dates for censoring is summarized in Table 2 as follows.

Table 2: PFS Event and Censoring Method

Situation	Date of Progression or Censoring	Outcome
Disease progression prior to start of	Earliest date that indicates disease progression	PFS event
subsequent antimyeloma therapy		
Death without subsequent antimyeloma	Date of death	PFS event
therapy		
No post-baseline disease assessment	Randomization	Censored
Other (e.g., withdrawal of consent to study	Date of last disease assessment prior to	Censored
participation, lost to follow-up, start of subsequent	withdrawal of consent to study participation, lost to	
antimyeloma therapy etc.)	follow-up, or subsequent antimyeloma treatment	
/	- · · ·	

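### One corrected calcium above ULN by Day 4 bars calcium-based progression for the whole study, even after calcium returns to normal

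*SAP*

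**What the plan says.** Primary PFS rests on the computerized algorithm (SAP 4.2). In Attachment 2, 1.1.1 g, calcium counts as progression when it reaches "corrected serum calcium >2.875 mmol/L or >11.5 mg/dL) that can be attributed solely to the PC proliferative disorder". Protocol Table 8 (9.2.1.1) has the same criterion: "Development of hypercalcemia (corrected serum calcium >11.5 mg/dL) that can be attributed solely to the PC proliferative disorder". Neither criterion, as worded, excludes subjects by baseline calcium.

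Attachment 2, 1.2.15 then adds an exclusion: "For subjects who have hypercalcemia at baseline, the program will never assess PD due to" development of hypercalcemia. A subject counts as hypercalcemic at baseline on "any corrected calcium value >ULN which occurs on or before Day 4". Part b applies the same ULN trigger to free-ionized calcium where no corrected values exist. Nothing in 1.2.15 ends the exclusion.

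For subjects with normal baseline calcium, 1.2.16 sets out confirmation, dating and a clinical review of attribution. That review covers progressions the program has identified.

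On censoring, SAP 4.2.1 says: "Subjects who start subsequent antimyeloma therapies for multiple myeloma without disease progression will be censored at the last disease assessment" before those therapies start. SAP 4.3.6.1 does the same for TTP.

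**The concern.** The bar is set at ULN, while the event it suppresses is defined at more than 11.5 mg/dL. A subject whose early calcium lay between the two has never met the protocol's progression threshold. If calcium then stays normal for many months and rises above 11.5 mg/dL because of myeloma, that is a new development in the ordinary sense of Table 8.

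The trigger takes any early value, including a screening value already normal by Cycle 1 Day 1. For M-protein, FLC, plasmacytomas and bone lesions, 1.2.6 uses the last pretreatment measurement instead. Early calcium can change quickly: the protocol permits a short emergency corticosteroid course before treatment (4.2) and bisphosphonates started in Screening (8.1.2).

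At stake is a mismatch between clinical progression and the primary endpoint. The site and sponsor establish PD by Table 8 and next therapy begins (Protocol 8.4). The algorithm may record no PD and censor the subject close to the true progression. That is informative censoring. The review in 1.2.16 d cannot recover the case, because the program never flags it.

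**Working it through.** **Inputs**
- Trigger and bar: SAP Attachment 2, 1.2.15.
- Threshold of 11.5 mg/dL: Attachment 2, 1.1.1 g and Protocol Table 8. Unit check: 11.5 / 4 = 2.875 mmol/L, as stated.
- 390 PFS events, HR 0.75, 80% power, two-sided 0.05: SAP 1.3. Interim planned at 234 events: SAP 1.4.
- ULN is not stated. I assume 10.1 or 10.5 mg/dL; the results below are the same for both.
- Not in the documents: *b*, the share of subjects barred by 1.2.15, and *h*, the share of PFS events in which calcium is the only or first criterion.

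**Step 1: the rule applied to example records.** Values are mg/dL. No other criterion is met and attribution to myeloma is accepted.

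| Values to Day 4 | After Day 4 | Later values | Table 8 | 1.2.15 now | Bar that lapses |
|---|---|---|---|---|---|
| 9.5, 9.6 | normal | 12.5, 12.6 | PD | PD | PD |
| 10.6, 9.6 | normal | 12.5, 12.6 | PD | not PD | PD |
| 11.4, 9.8 | normal | 12.5, 12.6 | PD | not PD | PD |
| 12.0, 9.8 | normal | 12.5, 12.6 | arguable | not PD | PD candidate |
| 11.4 | never at or below ULN | 11.6, 11.6 | arguable | not PD | not PD |

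Rows 1 to 3 have the same later course. A single early value separates row 1 from rows 2 and 3.

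**Step 2: dating.** Under 1.2.16 a, if another parameter shows PD within 56 days of a first hypercalcemic value, PD is dated to that calcium value. A barred subject gets the later date of the other parameter. So calcium-first progressions are delayed, and calcium-only progressions are missed.

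**Step 3: what stays open.** "The program computes the date of progression as the earliest date of any of the tests listed in Section 1.1.1", so M-protein, FLC where applicable, bone lesions and plasmacytomas still count. Also, "Development of plasma cell leukemia is considered as disease progression". Death without new therapy remains a PFS event (SAP Table 2).

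**Step 4: size.** The plan's own figure first. Schoenfeld: 4 × (1.960 + 0.842)² / (ln 0.75)² ≈ 380 events. Freedman's formula gives 385. Both are within 3% of 390. Power at 390 = Φ(½ × √390 × 0.2877 − 1.960) = Φ(0.881) = 0.811.

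Events affected = N × b × h, with b and h taken as independent. Assumed ranges: b 5% to 30%, h 0.5% to 5%.
- N = 390, low: 390 × 0.05 × 0.005 = 0.10. High: 390 × 0.30 × 0.05 = 5.85.
- N = 234, low: 234 × 0.05 × 0.005 = 0.06. High: 234 × 0.30 × 0.05 = 3.51.
- Power at the high end, counting every affected event as lost: 390 − 5.85 = 384.15 events, Φ(0.859) = 0.805.
- If one arm lost 0.30 × 0.05 = 1.5% of its events and the other none, HR 0.75 would read about 0.75 × 0.985 = 0.739 or 0.75 / 0.985 = 0.761.

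**The case against.** Several points on the other side stand.

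- The departure is disclosed. Attachment 2 calls its PD criteria identical to the protocol's, but points to section 1.2, which announces sponsor modifications.
- ULN has a precedent. Protocol 9.2.1.3 treats free ionized calcium above ULN as hypercalcemic for this study. Table 8 also requires development and sole attribution to the plasma cell disorder. Excluding subjects whose calcium stays raised from entry is therefore defensible.
- SAP 4.2.3.1 plans PFS on investigator-assessed progression, which does not use 1.2.15 and would capture these events. The analysis in 4.2.3.2 would not restore them: it removes censoring at new therapy but keeps the algorithm.
- An obvious remedy, the last pre-treatment value with an 11.5 mg/dL cut-off, creates doubtful events. A drift from 11.4 to 11.6 would qualify. So would a rebound after a screening value of 13.0 had been brought down to 9.8 by Cycle 1 Day 1.
- The algorithm is described as validated (SAP 4), so changing a rule means re-checking it.

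None of this justifies a bar that never lapses. Once calcium has returned to normal on treatment, the reasons for excluding persistently raised early calcium no longer apply.

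**Conclusion.** The point holds for one defect: the bar has no end. It concerns only progressions in which calcium is the sole or first criterion, in subjects with an early value above ULN.

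A reader might infer more, and the documents do not support it:
- That all later progressions in barred subjects are lost. The other routes and death without new therapy still count, and PD met later on another criterion before new therapy is delayed, not lost.
- That censoring falls on the start of new therapy. It falls on the last disease assessment before it.
- That the rule favours one arm. Events can only be lost or delayed, but the rule is the same in both arms and has no inherent direction for the hazard ratio.
- That the PFS conclusion is in doubt. On the assumed shares about 0 to 6 of 390 events are affected, or 0 to 3.5 of 234.

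The size is an assumption, since the documents give neither share. If early raised calcium makes later calcium-led progression more likely, the figure grows in proportion: doubling *h* among barred subjects gives at most 2 × 5.85 = 11.7 of 390. Some barred subjects will never have a normal value after Day 4, and the fix leaves them excluded.

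**What to change.** Keep the baseline exclusion and its ULN trigger, but let it lapse. In 1.2.15, replace the permanent bar with: *the program will not assess PD due to development of hypercalcemia until at least one corrected calcium at or below ULN has been recorded after Day 4; thereafter 1.2.16 applies.* Use the matching free-ionized wording for part b. Extend the opening of 1.2.16, now limited to subjects with normal baseline calcium, to subjects whose bar has lapsed, so that confirmation and attribution review apply to them.

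Protocol 3.1 says the interim PFS analysis serves as the primary analysis, and that analysis is complete. Do not replace its result. Report the corrected rule as a sensitivity analysis in the PFS update for the final CSR. List every subject excluded by 1.2.15 who later exceeded 11.5 mg/dL, with arm, dates, other criteria met, and event or censoring status. That list replaces the assumed shares with a count.

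Cost: one SAP rule, re-checking of the validated program, and a few more calcium-based candidates to review. A rebound after a documented normal on-treatment value would become a candidate; the existing confirmation and attribution steps are there to judge it.

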Blood and 24-hour urine samples will be collected as specified in the Time and Events Schedule until the development of confirmed disease progression. After subjects have completed 24 months of study treatment, the timing of collection for SPEP and UPEP (and the timing of collection of FLC for subjects with light chain multiple myeloma) will change from every 4 weeks to every 8 weeks. Disease progression based on 1 of the laboratory tests alone must be confirmed by at least 1 repeat investigation performed at least 1 day later. Disease evaluations will continue beyond relapse from CR until disease progression is confirmed. Serum and urine immunofixation test and serum free light chain assay will be performed at Screening and thereafter when a CR is suspected (when serum or 24-hour urine M-protein electrophoresis [by SPEP or UPEP] are 0 or nonquantifiable) or maintained. However, for subjects with light chain multiple myeloma, serum free light chain assay will be performed routinely. Serum immunofixation (IFE) assay samples will be split into 2 aliquots, with 1 reserved for potential follow-on testing if daratumumab interference with IFE is suspected. As daratumumab is a monoclonal IgG antibody, additional serum samples may be utilized to monitor for potential daratumumab interference with the IFE.

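### SAP Attachment 2 rule 1.2.16 c scores one unrepeated high calcium as progression, although the protocol's Table 8 footnote asks for two consecutive assessments and exempts only bone marrow

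*SAP*

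**What the plan says.** SAP 4.2 bases primary PFS on the computerized algorithm in SAP Attachment 2. For a subject with normal baseline calcium whose first progression criterion is a high calcium, rule 1.2.16 of that attachment works in sequence:

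- **a** looks for progression in other parameters over the next 56 days.
- **b** applies if there is none and a further calcium value exists: "If the second value also meets the criteria for hypercalcemia, the subject is assessed as PD".
- **c** applies if none exists: "If there is no more follow-up calcium value, then the subject is assessed as PD".
- **d** adds a safeguard, a check that the myeloma is the only cause: "Any PD identified through a), b) or c) will be flagged and reviewed by clinical to ensure that hypercalcemia can be attributed solely".

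On confirmation, the footnote to protocol Table 8 says: "All response categories (CR, sCR, VGPR, PR, and PD) require 2 consecutive assessments made at any time before the institution of any new therapy". It gives one exemption from confirmation: "Bone marrow assessments need not be confirmed". Hypercalcemia is one of the progression criteria in that table.

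Protocol 9.2.1.2 adds, for laboratory progression: "Disease progression based on 1 of the laboratory tests alone must be confirmed by at least 1 repeat investigation performed at least 1 day later". That sentence stands in the section on myeloma protein measurements.

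**The concern.** Rule c treats the absence of a confirming value as if it were confirmation. A high calcium at the last visit before a data cut, a withdrawal or a loss to follow-up has no later value, so it can enter primary PFS as an event on one measurement. If a normal value arrives afterwards, rule b governs instead, and by implication the event disappears at the next analysis. A rise in M-protein at the same last visit would not count, because SAP 1.2.3 asks for two consecutive values.

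What is at stake is whether the primary endpoint follows its protocol definition and stays stable between data cuts. Time to progression and duration of response use the same progression date. The final CSR analysis is to update efficacy, so the rule can still matter.

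**Working it through.** **1. The rules side by side**

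| Evidence of progression | Protocol | SAP Attachment 2 |
|---|---|---|
| M-protein, FLC | two consecutive (Table 8 footnote) | two consecutive (1.2.3) |
| Bone marrow | exempt (Table 8 footnote) | two consecutive (1.2.3, cited at criterion d) |
| Calcium, later value exists | two consecutive (footnote; no exemption) | second value must also be high (1.2.16 b) |
| Calcium, no later value | two consecutive (footnote; no exemption) | one value is enough (1.2.16 c) |

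Only in the last row does the SAP ask for less confirmation than the footnote. For marrow it asks for more.

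**2. How the SAP treats other unconfirmed progression.** Rule 1.2.3 accepts it only with corroboration: death from progression inside 30 days, or progression in the same parameter within 4 weeks after new therapy starts. Rule 1.2.16 c has no such condition. For urine M-protein (1.2.19 b), two consecutive values are needed before the rules on missing follow-up apply, and at the last step a missing fourth value means no progression. SAP 4.3.6.1 also defines time to progression by confirmed progression.

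**3. Whether the review in 1.2.16 d supplies confirmation.** It asks about cause. It can remove a high calcium that has another explanation, but it cannot show whether the value would have persisted on repeat.

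**4. Size.** The documents do not say how many events depend on rule c. Let D be the number of PFS events, p1 the share whose first evidence is hypercalcemia, and p2 the share of those with no later calcium. D is 234 (planned interim) or 390 (planned primary analysis), from SAP 1.3 and 1.4. The ranges p1 = 1–3% and p2 = 10–30% are assumptions.

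Affected events = D × p1 × p2:
- D = 234: 234 × 0.01 × 0.10 = 0.23, up to 234 × 0.03 × 0.30 = 2.11
- D = 390: 390 × 0.01 × 0.10 = 0.39, up to 390 × 0.03 × 0.30 = 3.51

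That is about 0 to 2, and 0 to 4.

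**5. Effect on power, for scale.** The plan's 390 events (HR 0.75, 80% power, two-sided 0.05, 1:1) reproduce within 3%:
- Schoenfeld: 4 × (1.960 + 0.842)² / (ln 0.75)² = 380
- Freedman: (1.960 + 0.842)² × (1.75 / 0.25)² = 385

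Power with D events is Φ(√D × |ln 0.75| / 2 − 1.960), with the hazard ratio held at 0.75:
- 390 events: 81.1%
- 386 events (4 censored): 80.7%
- 370 events (20 censored, a deliberately extreme 5%): 79.0%

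**The case against.** The best defence is that calcium is handled separately on purpose.

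- Protocol 9.2.1.3, the calcium section, has no repeat rule. Its test is that no other cause explains the value, and 1.2.16 d applies that kind of test.
- The documents do not demand a repeat for every kind of progression. Protocol 9.2.1.7 waives repeat imaging when radiographic progression is obvious. The SAP accepts site-reported bone lesions (1.2.9), new plasmacytomas (1.2.13) and plasma cell leukemia (1.2.21) without one.
- SAP 1.1.1 attaches the two-assessment rule to criteria a to d, not to hypercalcemia, and SAP 1.2 announces that it clarifies and modifies the criteria.
- Rule c is narrow, and calcium is scheduled every cycle for two years and then every 8 weeks until progression, so a missing later value should be uncommon.
- SAP 4.2.3.1 re-analyses PFS on investigator assessment, which does not use rule c.

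Much of this stands. A reader might infer from 9.2.1.2 that the protocol wants every laboratory progression repeated. The documents do not support that: marrow is exempt, and the sentence most naturally refers to the M-protein tests listed in its own section. It is supporting evidence only.

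What the defence does not do is exempt calcium from the Table 8 footnote, which names progression without limiting it to M-protein. A general notice of modifications does not create an exception that the protocol lacks. Rule b also undercuts the claim of a deliberate single-value design, since it asks for a second high value whenever one can be had. The investigator-based analysis changes every progression call at once, so it does not isolate this rule.

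**Conclusion.** The conflict is real and minor. Rule 1.2.16 c departs from the Table 8 footnote and from the SAP's own handling in 1.2.16 b and 1.2.3. The departure is limited by the normal-baseline condition, the 56-day search and the attribution review.

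On the assumed rates it touches about 0 to 2 of 234 events, or 0 to 4 of 390. The first figure is the more relevant, because the interim planned at 234 events became the primary PFS analysis. These counts rest entirely on the assumed 1–3% and 10–30%.

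A reader might go further and infer that the PFS result is biased or in doubt. Nothing in the documents shows an imbalance of such cases between arms, and even 20 reclassified events out of 390 would lower power only from 81.1% to 79.0%. The point concerns a consistent and stable endpoint definition, not the trial's conclusion.

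**What to change.** Align 1.2.16 c with 1.2.3. When no later calcium value exists, the high value is unconfirmed and the subject is censored at the last disease assessment, unless one of the 1.2.3 exceptions applies (death from progression inside 30 days, or the same parameter within 4 weeks after new therapy). A death without new therapy remains a PFS event under SAP Table 2.

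PFS superiority is already established, so the rule should not simply be deleted from the reported analysis. Keep the prespecified result, run the aligned rule as a sensitivity analysis, and list by arm each subject whose status or date changes.

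The cost is one line in the algorithm and a rerun. The drawback is that a few events become censored, possibly informatively: a subject whose last calcium pointed to progression, with no other cause found, is unlikely to have the same outlook as those still followed. That is a further reason to show both versions.
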